5.5 Dietary and Lifestyle Restrictions

Subjects must avoid phototherapy, excessive or prolonged sun exposure, or use of ultraviolet (UV) light sources within 28 days of randomization and throughout the study. Subjects will not otherwise alter their lifestyle and will not alter their diet during the study except to remain compliant with the inclusion and exclusion criteria.

6. STUDY TREATMENTS

6.1 Investigational Products and Controls

The study product under investigation in this study, PPC-06 (tepilamide fumarate) is a prodrug of MMF and a member of the FAE class of compounds. It will be administered as an extended release (ER) tablet formulation for oral administration via blister wallets during the Double-Blind Titration Period and via bottles during the Double-Blind Treatment Period. Three dosages of PPC-06 ER tablets (400 mg QD, 400 mg BID, and 600 mg BID) and a placebo BID regimen (using placebo tablets identical in appearance to the active-treatment tablets) will be studied.

PPC-06 ER tablets are white round tablets of 100 mg and 200 mg dose strength, and are manufactured and packaged under Good Manufacturing Practice (GMP) regulations. Tablets are formulated with PPC-06 and the following excipients: lactose, hypromellose, colloidal silicon dioxide, hydroxypropyl cellulose, and magnesium stearate.

The placebo tablets will contain the same ingredients as the active formulation(s) without the active ingredient, and will be identical in appearance to the active PPC-06 ER tablets. Depending on the dose group, subjects are expected to ingest 2.98g to 2.31g of lactose daily from study medication, which is approximately the amount of lactose in ¼ cup of whole milk.

6.2 Dosing Regimen

Dosages and pill allocations for the Titration Period (Weeks 1-5) and for the Treatment Period (Weeks 6-24) are shown in [Table 6-1](#) and [Table 6-3](#), respectively. The dosing regimen for the Titration Period is presented in [Table 6-2](#). Note: Doses specified in red followed by a 'P' indicate Placebo.

Double-Blind Titration Period (Baseline through Week 5)

Following completion of the pre-randomization Screening Period, eligible subjects will be randomized in a 1:1:1:1 ratio to 1 of the 4 treatment arms and will enter the 5-week Double-Blind Titration Period. The first dose of study drug will be taken the day after the Baseline Visit (on Day 1). If a subject misses a dose (or several doses) during the Titration Period, they should skip that dose and continue with the next scheduled dose. At least 4 hours should elapse between doses, but ideally 8-12 hour intervals should be maintained. If a subject misses 7 or more consecutive days of dosing during the Titration Period, the site should contact the Sponsor or designee for guidance on how to proceed. At Visit 3 (Week 4), the subjects will

be instructed to continue 1 more week of Titration dose (Week 5 of blister wallets) and will also be given a kit of bottles which will allow dosing until Visit 4. Please refer to [Table 6-1](#) for titration schedule.

Double-Blind Treatment Period (Week 6 through Week 24)

Subjects will receive PPC-06 400 mg QD, PPC-06 400 mg BID, PPC-06 600 mg BID, or Placebo BID from Week 6 through Week 24, based on the treatment arm to which they were randomized. Subjects will return to the clinic every 4 weeks (± 3 days) thereafter for drug accountability and to undergo safety and efficacy evaluations per the schedule of assessments ([Table 1-1](#)).

- Visit 4: End of Week 8
- Visit 5: End of Week 12
- Visit 6: End of Week 16
- Visit 7: End of Week 20
- Visit 8: End of Week 24
- Visit 9: End of Week 25

Table 6-1 Treatment Schedule - Titration Period (Weeks 1-5)

	400 mg QD	400 mg BID	600 mg BID	Placebo BID
Week 1 (Days 1-7)	100 P (am) + 100 P (am) 100 P (pm) + 100 (pm)	100 P (am) + 100 P (am) 100 P (pm) + 100 (pm)	100 (am) + 100 P (am) 100 P (pm) + 100 (pm)	100 P (am) + 100 P (am) 100 P (pm) + 100 P (pm)
Week 2 (Days 8-14)	200 P (am) + 200 P (am) 200 P (pm) + 200 (pm)	200 P (am) + 200 P (am) 200 P (pm) + 200 (pm)	200 (am) + 200 P (am) 200 P (pm) + 200 (pm)	200 P (am) + 200 P (am) 200 P (pm) + 200 P (pm)
Week 3 (Days 15-21)	100 P (am) + 100 P (am) 200 (pm) + 200 (pm)	100 P (am) + 100 (am) 200 P (pm) + 200 (pm)	100 (am) + 100 (am) 200 (pm) + 200 (pm)	100 P (am) + 100 P (am) 200 P (pm) + 200 P (pm)
Week 4 (Days 22-28)	200 P (am) + 200 P (am) 200 (pm) + 200 (pm)	200 P (am) + 200 (am) 200 P (pm) + 200 (pm)	200 (am) + 200 (am) 200 (pm) + 200 (pm)	200 P (am) + 200 P (am) 200 P (pm) + 200 P (pm)
Week 5 (Days 29-35)	200 P (am) + 200 P (am) 200 (pm) + 200 (pm) + 200 P (pm)	200 P (am) + 200 (am) 200 (pm) + 200 (pm) + 200 P (pm)	200 (am) + 200 (am) 200 (pm) + 200 (pm) + 200 (pm)	200 P (am) + 200 P (am) 200 P (pm) + 200 P (pm) + 200 P (pm)

Table 6-2 Titration Regimen

Visit	Weeks (Days)	Tablet regimen for all groups
Baseline*	Week 1 (Days 1-7)	Take 2 tabs in the morning and 2 tabs in the evening from the blister
	Week 2 (Days 8-14)	Take 2 tabs in the morning and 2 tabs in the evening from the blister
	Week 3 (Days 15-21)	Take 2 tabs in the morning and 2 tabs in the evening from the blister
	Week 4 (Days 22-28)	Take 2 tabs in the morning and 2 tabs in the evening from the blister
	Week 5 (Days 29-35)	Take 2 tabs in the morning and 3 tabs in the evening from the blister
Week 4# (Day 28)	Week 6 (Days 36-42) to Week 8 (Days 50-56)	Take 1 tab from AM Bottle 1 and 2 tabs from AM Bottle 2; repeat the process in the night with PM bottles.

* = Subjects will be given 5 blister wallets (for Weeks 1-5)

= Subjects will be given 2 sets of 2 Bottles as mentioned.

Table 6-3 Treatment Schedule: Treatment Period (Weeks 6-24)

Visit	PPC-06 400 mg QD Regimen	PPC-06 400 mg BID Regimen	PPC-06 600 BID Regimen	PPC-06 Placebo BID Regimen
	Week 6 – Week 24	Week 6 – Week 24	Week 6 – Week 24	Week 6 – Week 24
Weeks 8-20 (Dispense 2 sets of 2 Bottles) ¹	200 P (am) + 200 P (am) + 200 P (am) 200 (pm) + 200 (pm) + 200 P (pm)	200 P (am) + 200 (am) + 200 (am) 200 (pm) + 200 (pm) + 200 P (pm)	200 (am) + 200 (am) + 200 (am) 200 (pm) + 200 (pm) + 200 (pm)	200 P (am) + 200 P (am) + 200 P (am) 200 P (pm) + 200 P (pm) + 200 P (pm)

¹ Subjects will be given 2 sets of 2 bottles (2 morning (AM) bottles + 2 evening (PM) bottles)

AM Bottles: AM Bottle 1 (30 count) and AM Bottle 2 (60 count)

PM Bottles: PM Bottle 1 (30 count) and PM Bottle 2 (60 count)

Take 1 tablet from (AM) Bottle 1 and 2 tablets from (AM) Bottle 2; repeat the process in the evening with (PM) bottles

6.3 Dose Modification

At any point during the Double-Blind Titration or Treatment Periods, a temporary dose reduction or interruption may be considered in circumstances where a subject has a tolerability issue such as flushing or GI intolerance. The Investigator may use other medications such as loperamide for diarrhea (or local standard of care) for tolerability management as long as the medication is not one of the prohibited/restricted medications.

During the Double-Blind Treatment Period (Weeks 6-24), in the event of a temporary dose reduction (no more than 2 weeks), 1 tablet from each Bottle 2 (AM and PM) will be reduced. When the tolerability issues resolve, study drug should be titrated back up to the respective treatment dose. If the tolerability issues return at the higher dose, subjects may be discontinued from the study.

Note: Subjects who discontinue study treatment for more than 2 weeks during the Double-Blind Titration or Treatment Periods due to tolerability issues or for any other reason at any point during the study will not be allowed to resume their study treatment and will be scheduled for an ETV. Subjects who discontinue from the study for any reason at any time point will directly continue to the ETV.

6.4 Packaging and Labeling

The IP will be labeled according to all applicable federal regulations and be printed in the local language.

The study medication will be supplied to the clinical site(s) in kits containing 5 weeks of blister wallets which will be used for the Titration Period, as well as kits containing 2 sets of 2 Bottles which will be used for the Treatment Period. The blister wallet kits will contain a total of 147 tablets, and the Bottle kits will contain 2 AM and 2 PM bottles:

- AM Bottle 1 – 30 tablets
- AM Bottle 2 – 60 tablets
- PM Bottle 1 – 30 tablets
- PM Bottle 2 – 60 tablets

6.5 Storage

Investigational product must be stored at controlled room temperature (20-25°C, 68-77°F) with excursions permitted to 15°-30°C (59°-86°F). Subjects will be advised to keep study medication out of reach of children and persons who may not be able to read or understand the label. All study medication should be kept in a secure area inaccessible to unauthorized individuals.

All remaining IP will be returned to the sponsor or its designee after final drug accountability has been completed.

6.6 Assignment to Treatment

6.6.1 Randomization

All subjects who enter into the screening period for the study (defined as the point at which the subject signs the ICF) will receive a subject identification number through the Interactive Web Response System (IWRS). This number (which will consist of the site number followed by the subject number) will be used to identify the subject throughout the study and must be used on all study documentation related to that subject. The subject identification number must remain constant throughout the entire study; it must not be changed at the time of screening or randomization. This number will not be the same as the assigned randomization number. The IWRS will be used for randomization. A subject can be rescreened on a case by case basis with input from the Medical Monitor. In the event a subject is rescreened, the subject will be (re)presented with the ICF and a new subject identification number will be given by IWRS.

Once assigned to a subject, a subject identification number will not be reused. If the subject fails to be randomized for any reason, the reason for not being randomized will be entered in the subject's eCRF.

The randomization scheme will be reviewed and approved by a member of the sponsor's Biostatistics and Data Management (BDM) group or designee. The sites will randomize eligible subjects by contacting IWRS at Visit 2 after all of the relevant Baseline procedures are completed and assessed as appropriate. A subject who fulfills the study eligibility requirements will be randomly assigned to treatment. The randomization will be stratified by prior biologic use.

The IWRS will assign a randomization number to the subject, which will be used to link the subject to the treatment group and will specify a unique Blister Wallet IP kit number for the IP to be dispensed to the subject at Visit 2 for the Titration Period. The sites will log in to IWRS during each subsequent subject visit to obtain the kit numbers of the Bottle Kits to be dispensed at study Visits 3-7.

6.6.2 Blinding

This is a double-blind study. The investigator, study coordinator(s), subjects and the Sponsor study team and its representatives, will be blinded to the identity of the randomized treatment assignment from the time of randomization until database lock. Randomization data will be kept in strict confidence by the statistician who generated the randomization schedule, the IWRS provider, and the vendor involved in the IP labeling. All active and placebo IP will be of identical appearance, regardless of the dose. Study materials will be packaged and issued in a manner designed to maintain the blind.

Unblinding by study site personnel for AEs should only be performed in an emergency, when knowledge of the subject's treatment assignment is essential for the clinical management or welfare of the subject ([Section 13.1](#), Emergency Unblinding).

Prior to unblinding, the investigator should make every effort to first contact the Medical Monitor (or designee) and should assess the relationship of an AE to the administration of the IP. The investigator must then log in to the IWRS to unblind the individual subject's treatment assignment. If the blind is broken for any reason, the investigator must record the date and reason for breaking the blind on the appropriate eCRF and source documents.

For details of the procedure for unblinding of individual subjects in cases of emergency see [Section 13.1](#).

6.7 Prior and Concomitant Therapy

All medications, including over-the-counter (OTC) drugs, taken within 30 days prior to the start of the study (Screening Visit) will be recorded at Screening. Thereafter, a record of all medications and supportive therapy taken during the course of the study will be made. Information regarding the total daily dose, route of administration, start and discontinuation dates, and indication are to be recorded on the subject's eCRF.

Changes to medications, including prescription, OTC, herbal preparations, or mineral supplements taken for treatment of psoriasis will not be allowed without prior approval of the Medical Monitor or designee. Use of hormonal contraceptives is to be stabilized for at least 3 months prior to randomization.

The use of non-medicated emollients is permitted during the study; every effort is to be made to maintain the same regimen following Screening and throughout the study. The use of color-cosmetics and sunscreens/sunblocking agents is allowed; however, excessive and/or prolonged exposure to direct sun must be avoided during the trial.

The use of non-steroidal anti-inflammatory drugs (NSAIDs) or analgesic treatments will be permitted to treat symptoms of psoriatic arthritis on a PRN basis.

Restrictions regarding prior and concomitant therapies, as listed in the Exclusion Criteria, must be observed during the study, including the treatment and follow-up periods. Dose adjustments of any permitted concomitant medications should be avoided during the study, if possible.

The following therapies are prohibited from use at any time during the study:

- Any drug known to influence the course of psoriasis such as lithium, beta-blockers, and antimalarial therapies
 - Stable doses of beta-blockers are permitted if there is no history of exacerbation of psoriasis due to beta-blockers and the dose will be kept unchanged throughout the trial.

- Any live vaccines, except flu vaccines.
- Any systemic non-biologic immunosuppressive medication (eg, MTX, cyclosporine, mycophenylate mofetil, 6-thioguanine)
- Biologic agents (eg, etanercept, alefecept) and any antibody (eg, infliximab, adalimumab, golimumab, ustekinumab)
- Any systemic steroid (steroid inhalers, nasal sprays and eye drops or intra-articular injections are permitted)
- Phototherapy
- Laser therapy for psoriasis or other skin conditions
- Topical corticosteroids (other than the limited use of mild topical steroids specified below under "Rescue Medication"), vitamin D analogs, tar preparations, salicylic acid, or urea preparations
- Topical or systemic calcineurin inhibitors (eg, tacrolimus, pimecrolimus)
- Topical or systemic retinoids (eg, tazarotene, tretinoin, adapalene)
- Topical (ointment and/or baths) or oral fumaric acid derivatives
- Cytostatic drugs (eg, cyclophosphamide, ifosfamide, vinblastine, vincristine, procarbazine, dacarbazine, 6-mercaptopurine, 5-fluorouracil, adriamycin)
- Any investigational drug or therapy, or approved drug or therapy for investigational use

Rescue and Concomitant Medication

The use of rescue medications for the treatment of psoriasis may be permitted during the Double-Blind Titration and/or Treatment Period at the investigator's discretion. Subjects will be considered a treatment failure if rescue therapy is required; however, they can continue for safety monitoring, if required. Concomitant medications permitted for use for psoriasis are restricted to bland emollients and other non-medicated interventions. This excludes any topical agents that contain pharmacologically active ingredients (eg, salicylic acid, alpha-hydroxy acids, urea, etc.). Dose adjustments of any permitted concomitant medications should be avoided during the study, if possible.

Note: Limited use of mild topical steroids (Class VI or VII in North America) for the treatment of psoriasis on limited areas (face, axilla, and/or genitalia) is permitted. Subjects will be permitted to use medicated shampoos (on the scalp only in the shower). This will not be considered as rescue medication.

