The imputation of missing post-baseline BSA, PSSI final score, NAPSI, and NRS scores will be performed using a similar method as described for PASI. The imputation of missing post-baseline PP PGA scores will be performed using a similar method as described for IGA. A pre-specified seed number of 132138 will be used in all imputation procedures. No imputation will be done to the health-related quality of life endpoints or safety endpoints.

- **Observed cases (OC)**: No imputation will be performed, only observed values will be analyzed.
- **m-NRI (response endpoint only)**: Subjects who used rescue medications or discontinued due to unsatisfactory therapeutic effect are considered as treatment failures (i.e., non-responder) for all time points after the initiation of rescue medications or subject discontinuation. For example, if a subject discontinued due to lack of efficacy, all visits

after the last planned visits will be imputed to non-responders. If a subject used rescue medication during the study, all visits after the start of the rescue medication will be imputed to non-responders regardless if the subject had an assessment or not. Other subjects with missing data will be kept as missing (i.e., no imputation). Discontinuation due to unsatisfactory therapeutic effect will be identified by discontinuation reason = "Other" with a comment "lack of efficacy" on the eCRF.

- **LOCF:** The last observed value will be carried forward for any subsequent missing values. Baseline values will not be carried forward.

A summary of the imputation methods for all efficacy endpoints is shown below:

Endpoint	Analysis Population	Imputation Methods
PASI-75 at Week 24	FAS	MI, m-NRI, LOCF, OC
	PP	m-NRI
IGA score of clear or almost clear at Week 24	FAS	MI, m-NRI, LOCF, OC
	PP	m-NRI
Change from Baseline and percent change from Baseline in PASI Total Score by Visit	FAS	MI, LOCF, OC
	PP	OC
PASI-50 and PASI-75 by Visit	FAS	MI, m-NRI, LOCF, OC
	PP	m-NRI
IGA score of clear or almost clear by Visit	FAS	MI, m-NRI, LOCF, OC
	PP	m-NRI
Change from Baseline and percent change from Baseline in BSA by Visit	FAS	MI, LOCF, OC
	PP	OC
Change from Baseline in NPSI by Visit	FAS	MI, LOCF, OC
	PP	OC
Change from Baseline in PSSI by Visit	FAS	MI, LOCF, OC
	PP	OC
Change from Baseline in PP PGA by Visit	FAS	MI, LOCF, OC
	PP	OC
Change from Baseline in NRS by Visit	FAS	MI, LOCF, OC
	PP	OC
Time to PASI-75	FAS	OC
Time to achieving an IGA score of clear or almost clear	FAS	OC
QIDS-SR 16	FAS	OC

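### Protocol 6.7 permits rescue medication but leaves no active agent both allowed and counted as rescue, so FAS m-NRI results depend on an undefined label

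*Protocol*

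**What the plan says.** Protocol 6.7, Rescue and Concomitant Medication, opens: "The use of rescue medications for the treatment of psoriasis may be permitted during the Double-Blind Titration and/or Treatment Period", and leaves this to the investigator. The consequence follows: "Subjects will be considered a treatment failure if rescue therapy is required; however, they can continue for safety monitoring, if required". No rescue agent is named.

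Three other statements in 6.7 bear on this:

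- **Prohibited list.** It begins: "The following therapies are prohibited from use at any time during the study". It covers systemic immunosuppressants, biologics, systemic steroids, phototherapy, topical corticosteroids beyond limited mild use, vitamin D analogs, tar, salicylic acid, urea, calcineurin inhibitors and retinoids, among others. It states no exception for rescue.
- **Psoriasis medication generally.** "Concomitant medications permitted for use for psoriasis are restricted to bland emollients and other non-medicated interventions".
- **Note on allowed active topicals.** It permits "Limited use of mild topical steroids (Class VI or VII in North America) for the treatment of psoriasis on limited areas" and medicated shampoos on the scalp, and says that this is not rescue. The prohibited list nevertheless points to the mild-steroid exception as lying under the rescue heading.

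SAP Section 9, m-NRI: "If a subject used rescue medication during the study, all visits after the start of the rescue medication will be imputed to non-responders". This applies whether or not the subject was assessed. Other subjects' missing data stay missing, and nothing is said about data observed after a prohibited drug.

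SAP Section 8 lists prohibited medication as a major violation, which excludes the subject from PP. It also says that rescue users are kept in PP as treatment failures.

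Listing 16.2.4.2 carries a yes/no rescue column. Neither document says how it is decided.

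**The concern.** No active agent is identified that is both permitted and counted as rescue. A site that gives a subject an active psoriasis drug can record it as rescue or as a deviation, and the text supports either.

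That choice matters because m-NRI is the only planned FAS analysis that carries out the treatment-failure statement in 6.7. It is a sensitivity analysis for both co-primaries and one of the methods for the responder endpoints by visit. It is also the only PP method for the co-primaries, and one of three used in the blinded interim summaries (SAP Section 10). If the classification is undefined, the result of that check depends partly on how sites fill in a field.

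**Working it through.** **1. The plan's own figure.** Inputs from Protocol 8.2 and SAP Section 7: 15% versus 45%, about 50 completers per arm, two-sided 0.05, chi-squared test. With pooled variance under the null:

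- Null SE = sqrt(2 x 0.30 x 0.70 / 50) = 0.0917
- Alternative SE = sqrt((0.15 x 0.85 + 0.45 x 0.55) / 50) = 0.0866
- Power = Phi[(0.30 - 1.96 x 0.0917) / 0.0866] = Phi(1.39) = 0.918 per endpoint
- Two co-primaries, treated as independent: 0.918 squared = 0.842

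This reproduces the stated figure of at least 84%. It uses no rescue assumption, so the label does not alter it.

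**2. The same subject under each label.** Take a subject who receives a drug on the 6.7 prohibited list for psoriasis and is assessed at Week 24.

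| Analysis | Labelled rescue | Labelled deviation |
|---|---|---|
| FAS, MI (primary) | Observed result kept | Observed result kept |
| FAS, OC | Observed result kept | Observed result kept |
| FAS, LOCF | Observed result kept | Observed result kept |
| FAS, m-NRI | Non-responder | Observed result kept |
| PP, m-NRI | Included as failure | Excluded |

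MI fills missing values only and has no failure rule for rescue, so with the same recorded assessments it gives the same result under either label. The label acts only in the last two rows. In PP, a rescue drug that is also on the prohibited list meets both the exclusion rule and the inclusion rule, and SAP Section 8 does not say which takes precedence.

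**3. Illustrative size in FAS m-NRI.** Assumed, not in the documents: a share f of placebo subjects use such a drug and are assessed at Week 24, a share q of them respond, and the rest respond at the plan's 15%.

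- All labelled rescue: 0.15 x (1 - f)
- None labelled rescue: 0.15 x (1 - f) + f x q
- Shift due to the label: f x q

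| f | q | All rescue | None rescue | Shift (points) |
|---|---|---|---|---|
| 5% | 30% | 14.3% | 15.8% | 1.5 |
| 5% | 50% | 14.3% | 16.8% | 2.5 |
| 10% | 30% | 13.5% | 16.5% | 3.0 |
| 10% | 50% | 13.5% | 18.5% | 5.0 |
| 20% | 30% | 12.0% | 18.0% | 6.0 |
| 20% | 50% | 12.0% | 22.0% | 10.0 |

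**4. Effect on the comparison.** If f and q are equal in both arms, the f x q term cancels and the rate difference is 0.30 x (1 - f) under either label. The odds ratio, which the SAP reports, still moves. At f = 20% and q = 50%, the active rate is 0.45 x 0.80 = 36% (all rescue) or 36% + 10% = 46% (none). The unadjusted odds ratio is (0.36/0.64)/(0.12/0.88) = 4.1 or (0.46/0.54)/(0.22/0.78) = 3.0.

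**The case against.** **Rescue as an implied exception.** The rescue paragraph can be read as a penalised exception to the restrictions: the drug may be given, and the price is treatment failure. SAP Section 8 also treats rescue and prohibited use as separate categories. This reading is coherent, but it is not written. Even if accepted, nothing says which use of a listed drug is rescue and which is a deviation.

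**Not every active therapy is banned.** This is right: limited mild steroids and medicated shampoos stay allowed. The first item on the list, "Any drug known to influence the course of psoriasis such as lithium, beta-blockers, and antimalarial therapies", is also not clearly a ban on treatments, since its sub-item concerns exacerbation by beta-blockers. The point does not rest on that item. The enumerated classes are broad, and the allowed topicals are declared not to be rescue.

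**Other controls exist.** Indication and dates are recorded, changes to psoriasis medication need prior approval from the Medical Monitor or designee, and deviations and PP membership are settled before unblinding. These supply the information for a correct classification but do not define the rescue flag.

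**It is only a sensitivity analysis, and PP m-NRI already bars such responders.** Both statements stand, and they limit the point to robustness.

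**Conclusion.** The point holds as a conflict within Protocol 6.7 that passes into one FAS method and, as failure versus exclusion, into PP. It rests on the text and needs no assumption about usage. The shift of 1.5 to 10 points in the placebo m-NRI rate is illustrative only: the rates of use and response are assumed, and it compares the extremes of every user labelled rescue and none.

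A reader might infer three stronger things that the documents do not support.

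- **That the primary result is at risk.** The primary MI analysis has no rescue failure rule, so the label cannot change it.
- **That up to 85% of placebo subjects (the complement of the 15% response rate) are affected.** That equates every non-responder with a rescue candidate. It describes possible eligibility, not an effect on any estimate.
- **That power collapses.** If 20% of placebo non-responders used such a drug, half of them responded, none were labelled rescue and no active subject did the same, placebo response would be 0.15 + 0.85 x 0.20 x 0.50 = 23.5%. Exact single-endpoint chi-squared power at 50 per arm would fall from 92% to 63%. That is the extreme corner of assumed ranges (5-20% use, 30-50% response). Equal behaviour by active non-responders over those ranges gives 91% to 81%, and m-NRI has no power target.

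The direction of any bias is also not established, because the documents do not say in which arm use would be higher.

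**What to change.** 1. **Protocol 6.7.** Reconcile the rescue paragraph, the prohibited list (including its cross-reference to the mild-steroid exception) and the sentence restricting psoriasis medication. Which drugs should be allowed is for the sponsor to decide.
2. **SAP Section 9, before unblinding.** Define m-NRI failure on the FAS as starting from the first use of any therapy prohibited by 6.7 and given for psoriasis. Identify it by blinded review of recorded medication, indication and dates, regardless of the rescue flag. Exclude the mild steroids and medicated shampoos that 6.7 permits.

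The cost is a protocol clarification, a short SAP addition, and use of data and a blinded review that are already planned. The downsides are slightly lower m-NRI response rates and that brief use of a minor listed topical would also count as failure in this sensitivity analysis. The primary analysis stays as it is.
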